4.8.1.1. Propensity score methods

The PS is the probability of being exposed given the covariate pattern for the patient. The PS will be estimated for each patient hospitalization in each of the examined comparisons using a logistic regression model including calendar time and the covariates listed in the Appendix. As we are interested in the average treatment effect in the treated (ATT), we apply PS-weighting using ATT weights to make the number and covariate distribution in the comparison groups resemble that of the ACE-I/ARB users.

8

Overlap in PS distributions will be checked before weighting. Covariate balance will be assessed by standardized differences (SDs), empirical cumulative distribution functions for continuous variables (age and index), and by PS-weight percentiles.

4.8.2. Selection bias

The risk of selection bias is reduced by including all tested Danish inhabitants. Still, criteria for testing and hospital admission have changed during the study period, which will be addressed in a sensitivity analysis stratified by calendar time. We do not expect that ACE-I/ARB users would be more likely to be tested, and thereby included, as compared to users of other antihypertensive drugs.

4.8.3. Information bias

There may be some misclassification of the exposure, which will be addressed in a sensitivity analysis as described. Any misclassification is not expected to be associated with the outcomes of interest (non-differential misclassification), and any information bias are therefore expected to be towards the null.

As outcomes are accurately recorded, any misclassification is expected to be minor and not associated with the exposure.

4.9. Statistical analyses

In the analyses of prognosis, patients will be followed from day of SARS-CoV-2 positive test result and until date of hospital admission, ICU admission (in analysis of ICU admission), date of death, end of follow-up or for up to 30 days.

Patient characteristics will be tabulated according to each exposure group.

Descriptive analyses will explore the timing of outcomes one month prior to and three months after the first positive test for SARS-CoV-2. In case of a substantial fraction of outcomes having occurred in the days leading up to a positive test, a post-hoc analysis with a larger follow up windows (pre- and post-test) will be conducted.

For each exposure group, we will estimate the 30-day PS-weighted cumulative incidence (risk) of of death, and of each of the non-fatal events (hospital admission, ICU admission, ICU+MV, ICU+inotropes/vasopressors, RRT) accounting for competing risk by death. All 95% confidence intervals will be computed using bootstrapping. The risk of each outcome within 30 days will be computed with 95% CI.

Propensity scores for each comparison (e.g. current ACE-I/ARB use vs. current CCB use) will be computed using logistic regression including all the potential confounders as described above. All other exposures (anti-hypertensive drugs) will be included in the PS-model. The propensity score weighted (SMRW=ATT) cumulative incidence (risk) of each outcome will be plotted and estimated with 95% CI estimated by bootstrapping. The adjusted (PS weighted) risk difference will be computed for the 0-30 period.

The 30-day risk will be compared using PS weighted log binomial regression to estimate risk ratio for death, hospital admission, ICU admission, ICU+MV, RRT, and ICU+inotropes/vasopressors.

Subgroup analysis will be conducted to address effect modifiers including age group (=<65, >65 years) and in patients with assumed uncomplicated hypertension as the primary indication for treatment, defined as patients without any history of diabetes, renal disease, angina pectoris, myocardial infarction, or heart failure. We will also stratify by ABO blood type, if available, because blood type is suggested to be associated with ACE2.³⁰

The risk of COVID-19 (a positive test for SARS-CoV-2) will be analyzed using a testnegative case-control design among all patients tested. All covariates will be tabulated for patients with a positive test and negative test for SARS-CoV-2. The odds ratio for current ACE-I/ARB use vs. non-use and CCB use, respectively, will be estimated using two separate logistic regression models adjusted for all covariates, see Appendix.

In a sensitivity analysis, we will explore the robustness of our findings by repeating the analyses in patients who filled a prescription within 120 days before a positive test.

Finally, we will do a sensitivity analysis stratified by calendar time to address changes in testing and hospitalization strategy.

10

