4.5. Follow-up

Patients will be followed from the date of the first RT-PCR test for SARS-CoV-2 that turns out to be positive and up to 30 days after that date for all the outcomes. In a sensitivity analysis follow-up for hospitalization will be restricted to 14 days after first positive test.

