4.7. Outcomes

The primary outcome is death within 30 days after positive test for SARS-CoV-2, obtained from the Danish Register of Causes of Deaths.²⁷

Secondary outcomes include hospital admission (in- or acute outpatient stay lasting > 12 hours) at day of or within 30 days after a positive test in patients not already admitted before the date of the test. In addition, outcomes include ICU admission, mechanical ventilation, and renal replacement therapy at day of or within 30 days after positive test for SARS-CoV-2. Secondary outcomes will be obtained from the Danish National Registry, 3rd version (LPR3).²⁴ While the coding has not yet been validated in this LPR3, admission to ICU, mechanical ventilation, and renal replacement therapy are all registered accurately (positive predictive values 96%-100%) in LPR2 as this is also the platform for mandatory reporting to the national database for quality of intensive care.^{28,29}

Finally, in the risk analysis, we identified patients with positive tests among all patients tested for SARS-CoV-2.

[figure not shown]

Figure illustrating the endpoints in the COVID-19 risk analysis and the endpoints in the COVID-19 prognosis analysis.

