4.10. Sample size considerations

As of 20 April 2020, there are 96,224 individuals tested for SARS-CoV-2 and 7,515 are tested positive. A total of 364 patients with a positive test have died (4.8%). The proportion of patients using ACE-I/ARB is expected to be 17% and the proportion using CCB is expected to be 7% based on data from a historical cohort of patients with influenza or pneumonia ([name] et al., article submitted).

Assuming a 30-day mortality of 4% in unexposed, we will have a power of 92% for detecting a RR of 1.2 with an alpha-level of 5% in the comparison of current ACE-I/ARB users with non-users. (EpiSheet).

5. Ethical/data protection issues

According to Danish law, registry-based studies do not require informed consent or ethical committee approval. Only aggregated data will be published.

All data are pseudonymized and stored at secured serves at the Danish Health Data Authority. Data management and analyses are performed through secure remote access to these servers. Data management and analyses will be conducted and checked by experienced researchers.

6. Plans for communication of study results

[figure not shown]
The study protocol will be registered in the EU PAS registry. Results will be communicated through international peer-reviewed journals and the website of the Danish Medicines Agency. Any evidence of adverse effects of ACE-I/ARB will be communicated to the Danish Medicines Agency.

7. Amendments and deviations

Any future amendments or deviations from the study protocol will be included in this section.

Figure. Study design diagram

Study design

Codes

	Source/	Look-	Inclusion codes	Exclusion
	coding	back		codes
Exposures (ATC codes)				
Number of antihypertensives	NPD/ATC	90d	0-5 (see below: ACE-I/ARB, CCB, Thiazides/diuretics, BB, other antihypertensives)	
ACE-I	NPD/ATC	90d	C09A, C09B	
ARB	NPD/ATC	90d	C09C, C09D	
Calcium channel blockers (CCB)	NPD/ATC	90d	C07FB, C08CA, C09BB, C09DB, C09DX01	
Thiazides/diuretics	NPD/ATC	90d	C03AA01, C03AA03, C03AB01, C03AB03, C03AX01, C03EA, C07B, C09BA, C09DA, C09DX01, C09DX03, C09XA52, C09XA54	C07BA06 C09BA04
Beta-blockers (BB)	NPD/ATC	90d	C07	
Other antihypertensives	NPD/ATC	90d	C02AC, C02CA, C03BA11, C09XA C02AB01	C09XA54
Outcomes				
ICU admission (procedure code)	DNPR/Procedure		NABE, NABB	
Mechanical ventilation (procedure code)	DNPR/Procedure		BGDA0	

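### Section 4.9 lists hospital admission, unqualified, as an end of follow-up in all prognosis analyses, which contradicts the 30-day follow-up for death and the other outcomes in 4.5, 4.7 and 4.9 itself

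*Protocol*

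**What the plan says.** Section 4.9 opens with one follow-up rule for the whole prognosis part. Its scope is general: "In the analyses of prognosis, patients will be followed from day of SARS-CoV-2 positive test result". Its end points are "until date of hospital admission, ICU admission (in analysis of ICU admission), date of death, end of follow-up or for up to 30 days". No outcome is excepted, and the only end point tied to a particular analysis is ICU admission.

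Other parts of the protocol describe follow-up differently:

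- Section 4.5 runs follow-up "up to 30 days after that date for all the outcomes", counted from the date of the first test that proves positive. It has no stop at admission.
- Section 4.7: "The primary outcome is death within 30 days after positive test for SARS-CoV-2".
- Section 4.7, non-fatal events: "outcomes include ICU admission, mechanical ventilation, and renal replacement therapy at day of or within 30 days after positive test".
- Section 4.7 restricts the hospital-admission outcome to events "in patients not already admitted before the date of the test". That restriction is not placed on the other outcomes.
- Later in section 4.9, 30-day weighted cumulative incidences are planned for death and for each non-fatal event, the latter "accounting for competing risk by death". Risk differences over days 0 to 30 and log-binomial risk ratios for the 30-day risk are also planned. Hospital admission is not named as a competing event.

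**The concern.** The opening rule of 4.9 and the outcome definitions cannot both be followed. Under the rule as written, someone admitted on day 3 who dies on day 12 leaves follow-up on day 3, and the death does not enter the primary analysis. For patients admitted after the test, the endpoint becomes death before any admission rather than death within 30 days. The same applies to ICU admission, ventilation, vasopressor treatment and renal replacement therapy that begin after the admission day.

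Two analysts could each point to the protocol and report different primary results. Admission also marks worsening disease, so stopping there would not be neutral for the cumulative incidences and risk differences. Section 4.8.2 says that admission criteria changed during the study period, so the effect of such a stop could also shift with calendar time.

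**Working it through.** **1. The follow-up statements side by side**

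| Place in protocol | Applies to | End of follow-up | Stops at hospital admission? |
|---|---|---|---|
| 4.5 | All outcomes | 30 days | No |
| 4.7, death | Primary outcome | 30 days | No |
| 4.7, ICU, ventilation, RRT | Secondary outcomes | Test day to day 30 | No |
| 4.9, opening rule | All prognosis analyses | Admission, ICU admission (its own analysis only), death, end of follow-up, day 30 | Yes, unqualified |
| 4.9, risk estimates | Death and each non-fatal event | 30 days, death as competing event for non-fatal events | No |

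The opening rule of 4.9 is the only entry that stops at admission.

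**2. Can the sentence be read so that it agrees with the rest?**

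- *The qualifier covers only ICU admission.* Hospital admission then ends follow-up in every analysis, including death. This conflicts with 4.5 and 4.7.
- *The qualifier covers both admission terms.* Death is then unaffected, but the ICU analysis would stop at hospital admission, before any ICU admission that begins on a later day. This also conflicts with 4.7.
- *Each admission term ends follow-up only in its own analysis.* This agrees with everything else, but the reader has to supply a qualifier that is not in the text.

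The list gives no outcome-specific end for ventilation, vasopressors or RRT under any of these readings.

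**3. Who would be affected under the literal rule**

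- Admitted on or after the test date: follow-up ends at admission. Section 4.7 counts an admission on the day of the test, so some of these patients would have follow-up of zero length.
- Already in hospital before the test date: the current stay began before follow-up, so no admission date need end it. Their deaths and ICU, ventilation and RRT events need not be lost.
- Never admitted: no effect.

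**4. Size**

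Inputs from section 4.10, as of 20 April 2020: "there are 96,224 individuals tested for SARS-CoV-2 and 7,515 are tested positive", and 364 deaths among the positives, given as 4.8%.

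The protocol's own figure reproduces: 364 / 7,515 = 0.0484, or 4.8%.

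Let *f* be the share of deaths that follow a post-test admission on a later day. The protocol does not give *f*, so the values below are assumptions.

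Deaths still counted = 364 × (1 − *f*)

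| *f* (assumed) | Calculation | Deaths counted |
|---|---|---|
| 0.3 | 364 × 0.7 | 255 |
| 0.5 | 364 × 0.5 | 182 |
| 0.7 | 364 × 0.3 | 109 |
| 0.9 | 364 × 0.1 | 36 |

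The 364 is a snapshot taken before the inclusion cut-off in 4.2 and is not stated to be a count of 30-day deaths. The table shows how sensitive the count is to *f*; it is not a forecast.

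**5. Which estimates the rule would reach**

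The cumulative incidence curves and the risk differences use time at risk, so a stop at admission acts on them directly. The log-binomial risk ratio uses a yes/no status at day 30 and has no censoring time. There, the literal rule could only be applied by coding admitted patients as event-free or by dropping them, and the protocol describes neither.

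**The case against.** The best defence is that the intent is plain from context. Sections 4.5 and 4.7 and the rest of 4.9 all point to 30 days for each outcome. If admission really ended every analysis, the separate ICU term would be largely redundant. The sentence therefore looks like a shortened list of outcome-specific stops with one qualifier missing. This stands as an account of how the sentence arose, and it argues against reading it as a deliberate choice to censor at admission. It does not make the sentence correct, because the agreeing interpretation needs words that are not there.

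Three stronger inferences are tempting, and the documents do not support them:

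- *That all in-hospital deaths and nearly all ICU, ventilation and RRT events would be lost.* Section 4.7 recognises patients already admitted before the test, and their events need not be lost. The share among the others is not given.
- *That the risk ratio would be biased by informative censoring because ACE-I/ARB users have a different admission threshold.* Nothing in the protocol establishes such a difference, and the planned log-binomial model has no censoring time. The censoring argument applies mainly to the cumulative incidences and risk differences.
- *That competing mortality has been overlooked.* Section 4.9 already plans for it.

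The start of follow-up is a minor matter. Section 4.9 refers to the day of the positive result, which can be read as the test date fixed in 4.5.

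**Conclusion.** The contradiction is real and concerns the primary outcome. As written, the opening rule of 4.9 ends follow-up at hospital admission in every prognosis analysis, against 4.5, 4.7 and the 30-day risks in 4.9 itself. Patients admitted after the positive test would have their later deaths and later ICU, ventilation, vasopressor and RRT events left out.

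The number lost cannot be derived from the protocol. Under an assumed 30% to 90% of deaths following a post-test admission, between about 255 and 36 of the 364 deaths would be counted. If the sentence is a drafting slip, as is likely, and the analysis follows 4.5 and 4.7, nothing is lost. It should still be corrected before analysis, because a stated rule that would give the wrong primary result if followed should not depend on the analyst to disregard it.

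**What to change.** Replace the opening follow-up sentence of section 4.9 with an outcome-specific rule, for example:

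*In each prognosis analysis, patients are followed from the date of the first positive test (section 4.5) to the first of the outcome under analysis, death or day 30. Hospital admission ends follow-up only in the analysis of hospital admission.*

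This gives ventilation, vasopressors and RRT their own end of follow-up and takes the start date from 4.5. Keep the planned handling of death as a competing event for the non-fatal outcomes. The cost is one sentence, recorded under section 7 as an amendment. It needs no new data and no additional analysis.

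### Section 4.9 prescribes bootstrap confidence intervals throughout with no exception for sparse events; if the 30-day risk in the CCB arm is about 1% or less, those intervals cover too little, and they degenerate at 0 to 3 events

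*Protocol*

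**What the plan says.** Protocol section 4.9 states the rule in general terms: "All 95% confidence intervals will be computed using bootstrapping". It repeats it for the propensity-score-weighted analysis, where the "cumulative incidence (risk) of each outcome will be plotted and estimated with 95% CI estimated by bootstrapping". The outcomes listed there include RRT and ICU stay with inotropes or vasopressors, as well as death and admission.

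For the contrasts, "The 30-day risk will be compared using PS weighted log binomial regression to estimate risk ratio for death, hospital admission" and the remaining outcomes. The test-negative odds ratios "will be estimated using two separate logistic regression models adjusted for all covariates, see Appendix". Neither sentence names an interval method of its own.

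The same section plans subgroups: "Subgroup analysis will be conducted to address effect modifiers including age group (=<65, >65 years". Section 4.10 gives the sizes: "there are 96,224 individuals tested for SARS-CoV-2 and 7,515 are tested positive", and "the proportion using CCB is expected to be 7" per cent. Section 4.6 makes CCB one of the two main comparators. Its only condition about sufficient numbers concerns analysing ACE-I and ARB separately. Nothing says what happens when an outcome or subgroup yields few events.

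**The concern.** A nonparametric bootstrap can only resample events that were observed. When an arm has a handful of events, the resampled risks are too concentrated and too low at the upper end. With no event, every resample returns zero. The plan applies this method to uncommon outcomes and to an age subgroup, in a comparator arm of a few hundred patients.

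At stake are the error bars for some secondary outcomes and for death in one planned subgroup. Section 6 sends results to journals and to the Danish Medicines Agency's website. A comparator risk printed as 0% (0 to 0) for a severe renal outcome claims a certainty that 526 patients cannot provide.

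**Working it through.** **Inputs from the protocol (section 4.10).** There were 7,515 test-positive patients as of 20 April 2020, of whom 364 had died (364/7,515 = 4.84%, agreeing with the stated 4.8%). The ACE-I/ARB share is 17% and the CCB share 7%.

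- ACE-I/ARB arm: 0.17 × 7,515 ≈ 1,278.
- CCB arm: 0.07 × 7,515 ≈ 526. Recruitment after 20 April would raise this; removing patients who also take ACE-I/ARB would lower it.

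**Assumptions (the documents give no figures).** The 30-day risk in the CCB arm ranges over 0.3–2%. For the younger subgroup, 40% of CCB users are taken to be aged 65 or under, so n = 0.4 × 526 ≈ 210. Weight variability is moderate, with effective sample size (Σw)²/Σw² of about 358 of 526 and 144 of 210.

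**Step 1: how few events?** Exact binomial, ignoring weights:

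| CCB arm | Risk | Expected events | P(0) | P(3 or fewer) |
|---|---|---|---|---|
| n = 526 | 0.3% | 1.6 | 21% | 92% |
| n = 526 | 0.5% | 2.6 | 7% | 73% |
| n = 526 | 1% | 5.3 | 0.5% | 23% |
| n = 526 | 2% | 10.5 | ~0% | 0.7% |
| n = 210 | 0.5% | 1.1 | 35% | 98% |
| n = 210 | 1% | 2.1 | 12% | 84% |
| n = 210 | 2% | 4.2 | 1.4% | 39% |
| n = 210 | 4% | 8.4 | ~0% | 3% |

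If the share aged 65 or under is varied from 20% to 60% at 1% risk, P(3 or fewer) runs from 98% to 61%.

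**Step 2: when does the interval degenerate?** With k events among n patients, a resample contains none with probability (1 − k/n)ⁿ ≈ exp(−k). For n = 526 this is 37%, 13%, 5% and 1.8% at k = 1, 2, 3 and 4.

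- A percentile upper limit for the risk ratio (CCB in the denominator) is infinite once this share exceeds 2.5%, which means k ≤ 3. At k = 4 and 5 the unweighted interval is finite, about 0.34 to 5.8 and 0.36 to 4.5 when the two risks are similar.
- At k = 0 the arm's risk interval is 0 to 0. The exact two-sided upper limit is 1 − 0.025^(1/526) = 0.70%.
- The risk-difference interval keeps positive width as long as the other arm has an event.

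**Step 3: coverage of the nominal 95% percentile bootstrap for the weighted CCB risk, n = 526.** One simulation refitted the propensity score in every resample (250 datasets × 250 resamples). The others used generated weights with lognormal(0, 0.6) variability (for example 600 × 600 and 800 × 500).

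| Assumed risk | Score refitted | Generated weights |
|---|---|---|
| 0.3% | 73% | 71–74% |
| 0.5% | 79% | 79–82% |
| 1% | 84% | 86–87% |
| 2% | 90% | 91–92% |

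In the assumed subgroup of 210, coverage was about 58–65% at 0.5% and 75–76% at 1%. For the risk difference at 0.3–1% it was about 82–90% overall, and 84–87% with the score refitted. At 8% risk, coverage of the arm's risk was about 94%.

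**Step 4: what is not affected.** At 4.8% mortality the whole CCB arm has about 0.048 × 526 = 25 deaths and the bootstrap behaves (risk-ratio interval about 0.65 to 1.67 when the risks are equal). In the comparison with non-users, that arm holds up to 7,515 − 1,278 = 6,237 patients, and the ACE-I/ARB arm expects 12.8 events at 1%. Only at the lowest assumed risk (0.3%: 3.8 events), or within the younger subgroup, does the ACE-I/ARB arm itself become sparse.

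**Step 5: the alternative.** A Wilson interval on the effective sample size, with the MOVER combination for the difference, covered 93–97% in these settings, including the runs with a refitted score. With no events its upper limit is z²/(n_eff + z²) = 3.84/(358 + 3.84) = 1.1%, in place of zero.

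**The case against.** The strongest reply is that this is detail for a statistical analysis plan. Bootstrapping is an ordinary choice for weighted cumulative incidences. The protocol names neither the type of bootstrap nor a rule for suppressing estimates, and both could be settled later. In part this stands: the infinite risk-ratio limit belongs to the percentile interval, which the protocol does not specify. But the protocol is not silent on the method. It prescribes bootstrapping for all intervals, so an analysis plan must either inherit the problem or depart from the protocol. The zero-event result holds for any nonparametric bootstrap.

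The general sentence sits in the cumulative-incidence paragraph, so it may not have been meant for the log-binomial and logistic models. That also stands as a possible reading. The risk intervals are covered on either reading.

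The remedy can be criticised because a Wilson interval on the effective sample size treats the weights as known. That is true in principle, but coverage stayed at 93–97% when the score was refitted. The threshold of 10 events is pragmatic, not derived.

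A reader might also infer three stronger things that the documents do not support:

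- That the plan's own figures make collapse the expected result for RRT versus CCB and for death at age 65 or under. The documents give only the arm size. At 2% RRT risk, or 4% mortality in the younger group, degeneracy is unlikely.
- That few events in general give zero width or infinite limits. Zero width needs exactly 0 events; an infinite ratio limit needs about 0–3.
- That a zero-width interval would read as no difference. It affects one arm's absolute risk. The interval for the difference is too narrow but normally has positive width.

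**Conclusion.** The concern holds in a limited form. As written, the rule yields intervals with coverage well below 95% for the weighted CCB risk, and moderately below for the risk difference, wherever the 30-day risk in that arm is about 1% or less. Such a risk is an assumption, plausible for RRT or for death at age 65 or under compared with CCB, and no figure in the protocol confirms or excludes it. The coverage figures also rest on the assumed weight variability and, for the subgroup, on the assumed 40% age share. The primary outcome in the whole cohort is not touched, and comparisons with non-users are little affected except at the lowest assumed risks. The rule should be amended because the change is small and the faulty intervals would overstate certainty on a safety question.

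**What to change.** Add a short sparse-data rule to section 4.9 and state the type of bootstrap:

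- Keep the bootstrap where both arms have adequate events, for example at least 10.
- Below that, report raw event counts. Give each weighted risk a Wilson interval with n replaced by (Σw)²/Σw². Form the risk-difference interval by MOVER: lower limit d − √[(p₁ − l₁)² + (u₀ − p₀)²] and upper limit d + √[(u₁ − p₁)² + (p₀ − l₀)²], where d = p₁ − p₀ and l, u are the Wilson limits.
- Give no risk ratio when an arm has no event.
- Say whether the bootstrap sentence is meant to cover the log-binomial risk ratios and the logistic odds ratios.

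The cost is a few sentences and a few lines of code. The downsides are two interval methods in one table, some risk ratios left unreported, and weights treated as known in the sparse cells.

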4.8. Bias

4.8.1. Confounding

Confounding will be handled by using propensity score (PS) methods. In addition, the use of an active comparator design reduce confounding by indication, as most users of the comparator are also likely to have hypertension as the indication for treatment. To further reduce confounding by indication, we will repeat the analyses after restriction to patients without history of heart or kidney disease, which are other indications for ACE-I/ARB use. Although we included a large number of coexisting conditions, life-style factors and co-medication, we cannot exclude the impact of unmeasured confounding, e.g., by severity of condition indication ACE-I/ARB treatment. As we lacked detailed data on severity of heart and renal diseases, we reduced confounding in a subgroup analysis of patients without any history of these diseases.

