Acute renal replacement therapy (RRT) (in patients without chronic RRT)	DNPR/Procedure		BJFD0	BJFD2 (any codes within prior 12 months)
Treatment with inotropes/vasopressors	DNPR/Procedure		BFHC92A, BFHC92B, BFHC92C, BFHC92D, BFHC92E, BFHC93A, BFHC93B, BFHC93C, BFHC95	
Covariates				
Age	CPR			
Sex	CPR			
Calendar time (before / after lockdown)	DNPR			
Hospital-diagnosed hypertension	DNPR/ICD-10	10y	110, 115	
Stable angina pectoris (without procedures)	DNPR/ICD-10	10y	120, 1251, 1259	121, 122, 123, 1200
Stable angina pectoris or CABG/PCI procedures	DNPR/ICD-10	10y	120, 1251, 1259	121, 122, 123, 1200
	DNPR/Procedure	10y	KFNA, KFNB, KFNC, KFND, KFNE, KFNF, KFNG, KFNH20	I21, I22, I23, I200 (any diagnosis during hospital contact with
				contact the proc

				or within 10
				years before
Myocardial infarction	DNPR/ICD-10	10y	121, 122, 123	
Heart failure	DNPR/ICD-10	10y	150	
Stroke	DNPR/ICD-10	10y	160, 161, 163, 164	
Atrial fibrillation/flutter	DNPR/ICD-10	10y	148	
Heart valve disease	DNPR/ICD-10	10y	105, 106, 107, 108, 109.8, 134-137, 139, 151.1A, Q22, Q23	
Venous thromboembolism	DNPR/ICD-10	10y	126, 1801, 1802, 1803	
Diabetes	DNPR/ICD-10	10y	E10, E11, E12, E13, E14, O24, G63.2, H360, N083	O24.4
	NPD/ATC	10y	A10A, A10B	
Chronic pulmonary disease	DNPR/ICD-10	10y	J40, J41-J44, J45–J47, J60–J67, J68.4, J70.1, J70.3, J84.1, J92.0, J96.1, J98.2, J98.3	
Markers of smoking (diagnoses or medications for tobacco smoking or	DNPR/ICD-10	10y	J41-J44, F17, Z716, Z720	
chronic obstructive pulmonary disease)				
	NPD/ATC	10y	R03, N07BA	
Obesity diagnoses or medications	DNPR/ICD-10	10y	E66	
	NPD/ATC	10y	A08	
Alcoholism-related diagnoses or medication for alcohol deterrent	DNPR/ICD-10	10y	DF10, DE244, DG312, DG621, DG721, DI426, DK292, DK70, DK852, DK860, DQ860, DZ502, DZ714, DZ721	F100
	NPD/ATC	10y	V03AA, N07BB	
Kidney disease diagnosis	DNPR/ICD-10	10y	112, 113, N00–N05, N07, N11, N14, N18–N19, Q61, N08, E102, E112, E142	
End-stage renal disease (kidney transplant or dialysis)	DNPR/Procedure	10y	BJFD2	
	DNPR/Surgery	10y	KKAS	
	DNPR/ICD-10	10y	T861, Z940	
Liver disease	DNPR/ICD-10	10y	B18, B150, B160, B162, B190, I85, K70, K71, K72, K73, K74, K760, K76.6	
Dementia	DNPR/ICD-10	10y	DF00, DF01, DF02, DF03, DG30, DG310B, DG311, DG318, DG319	
	NPD/ATC	10y	N06D	
Cancer (including metastatic cancer)	DNPR/ICD-10	10y	C00-C96, D459, D46, D471, D473, D474, D475, CxxxM	C44
Concurrent antihypertensive medication (see exposures)	NPD/ATC			

Statins	NPD/ATC	90d	C10AA, C10B

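### The restricted analyses are described as free of any history of infarction or heart disease, but the code table looks back only 10 years and omits old infarction (I25.2) and ischaemic cardiomyopathy (I25.5)

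*Protocol*

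**What the plan says.** Two restricted analyses are planned.

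- Section 4.9 describes a subgroup of "patients with assumed uncomplicated hypertension as the primary indication for treatment". To belong to it, a person must be "without any history of diabetes, renal disease, angina pectoris, myocardial infarction, or heart failure".
- Section 4.8.1 states: "we will repeat the analyses after restriction to patients without history of heart or kidney disease, which are other indications for ACE-I/ARB use". It then says of the missing severity data on heart and renal disease that "we reduced confounding in a subgroup analysis of patients without any history of these diseases".

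The code table at the end of the protocol (headed Codes, the Appendix cited in sections 4.8.1.1 and 4.9) holds the only operational definitions. It gives "Myocardial infarction DNPR/ICD-10 10y 121, 122, 123" and "Heart failure DNPR/ICD-10 10y 150". The leading digit 1 is the letter I as read from the PDF, so these are I21-I23 and I50. The stable-angina rows list I20, I25.1 and I25.9, one of them with CABG/PCI procedures added, again over 10 years. The only I42 code in the table is I42.6, in the alcohol row: "DF10, DE244, DG312, DG621, DG721, DI426".

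**The concern.** The text promises no history at all, while the table can show only that certain hospital codes are absent over the last 10 years. The infarction row holds the acute-episode codes. The ICD-10 code that records a past infarction, I25.2, is in no row, although the table takes I25.1 and I25.9 from the same block. The two gaps compound, because I25.2 is the code that could pick up an infarction older than 10 years.

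Section 4.8.1 restricts on heart disease because it is another reason to prescribe ACE-I/ARB. By that reasoning, missed heart disease may be commoner among ACE-I/ARB users than among CCB users or non-users, and part of the confounding that the restriction is meant to remove would remain. The same flags enter the propensity score (sections 4.8.1.1 and 4.9) and the test-negative models (section 4.9). None of the planned sensitivity analyses varies the covariate look-back.

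**Working it through.** The protocol gives no figure to reproduce here. The check is a comparison of text with codes, followed by a bound on the bias under stated assumptions.

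**Step 1. Text against table**

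| Condition | Codes in the table | Look-back | Catches I25.2, I25.5 or I42? |
|---|---|---|---|
| Angina | I20, I25.1, I25.9 (one row adds CABG/PCI) | 10 years | No |
| Myocardial infarction | I21, I22, I23 | 10 years | No |
| Heart failure | I50 | 10 years | No |

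A match by code prefix, which also covered the kidney-disease row, found no row for any of the three codes. I42.6 is flagged only as alcohol-related.

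Two kinds of patient therefore pass as having no cardiac history:
- those whose only cardiac code within 10 years is I25.2 or I25.5 (or I42, for the section 4.8.1 restriction);
- those whose infarction is more than 10 years old and who have no later listed code.

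A patient who also has I20, I25.1, I25.9, I21-I23 or I50 in the window is caught, subject to the exclusion codes of the angina rows. So is a patient with a listed revascularisation procedure, if the angina row that includes procedures is the one applied.

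**Step 2. Size of the bias**

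Let p1 and p0 be the shares of missed heart disease in ACE-I/ARB users and comparators, and m the mortality ratio for missed disease. With a true risk ratio of 1, the unadjusted bias factor is

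(1 + p1(m - 1)) / (1 + p0(m - 1)).

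None of the three inputs is in the documents. Assume p1 = 3-6%, p0 = 1-2% and m = 1.5-3.

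- All low: (1 + 0.03 × 0.5) / (1 + 0.01 × 0.5) = 1.015 / 1.005 = 1.010
- All high: (1 + 0.06 × 2) / (1 + 0.02 × 2) = 1.12 / 1.04 = 1.077
- Smallest contrast: (1 + 0.03 × 0.5) / (1 + 0.02 × 0.5) = 1.015 / 1.010 = 1.005
- Largest contrast: (1 + 0.06 × 2) / (1 + 0.01 × 2) = 1.12 / 1.02 = 1.098
- Equal shares: 1.00 for any m

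The range 1.01-1.08 pairs low with low and high with high. The extreme combinations of the same assumptions give 1.005-1.10.

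**Step 3. Scale**

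Section 4.10 sizes the comparison with non-users for a risk ratio of 1.2. On the log scale, ln 1.010 / ln 1.2 is about 5% of that target and ln 1.077 / ln 1.2 about 41%.

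For random error against CCB, take 7,515 positives, 17% ACE-I/ARB and 7% CCB from section 4.10, and assume its 4% mortality in both groups. Expected deaths are 7,515 × 0.17 × 0.04 = 51 and 7,515 × 0.07 × 0.04 = 21. The standard error of the log risk ratio is √(1/51.1 - 1/1,278 + 1/21.0 - 1/526) = 0.254, so the 95% interval runs from the estimate divided by exp(1.96 × 0.254), about 1.6, to the estimate multiplied by it. This is the unweighted full cohort; a restricted subgroup would be less precise.

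**The case against.** Several objections stand, and they set the weight of the point.

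- **Place in the plan.** A reader might take the restricted analyses as the main defence against confounding by indication. Section 4.8.1 does not support that: propensity-score methods come first, the active comparator second, and restriction is a further step. The primary result does not rest on it.
- **Cardiomyopathy.** A reader might infer that leaving out I42 contradicts the section 4.9 subgroup. It does not, because cardiomyopathy is not one of the five conditions named there. It bears only on the wider heart-disease restriction of section 4.8.1, for which no code set is given.
- **Adjustment.** The bias factor is unadjusted. The weights also use beta-blockers and other antihypertensives, loop diuretics, statins, aspirin, vitamin K antagonists, atrial fibrillation and valve disease, which would plausibly absorb part of any missed cardiac disease.
- **Direction.** Upward bias in the ACE-I/ARB risk ratio is plausible against CCB or no use. It is not shown for the comparison with beta-blockers, another cardiovascular drug class.
- **Random error.** A shift of 1-8% is small beside an interval factor of about 1.6.
- **Hedging.** The protocol calls the hypertension indication assumed and admits unmeasured confounding. That qualifies the indication, but does not tell the reader that any history means 10 years of selected codes.

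It may also be said that subgroup codes belong in the SAP, and section 4.9 indeed does not say which rows it uses. But the protocol itself fixes codes and look-back for these conditions and offers no other definition.

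**Conclusion.** The mismatch is real, and it is minor. The restricted sets are described as free of any history, but they are free only of certain hospital codes within 10 years, with I25.2 and I25.5 missing and, for the section 4.8.1 restriction, I42 as well. That the 10-year limit conflicts with the wording follows from the protocol alone; the meanings of the omitted codes come from ICD-10, the protocol's own coding system.

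The consequence is some residual confounding by indication in a supporting analysis, with the same patients unflagged in the propensity score. The factor of 1.01-1.08 rests wholly on assumed shares and an assumed mortality ratio, is unadjusted, and falls to 1.00 with equal shares. A reader might infer that a substantial group of patients treated for heart disease remains in the subgroup, or that the main risk ratio is biased upwards. The documents give neither the number of such patients nor their treatment, so neither inference is supported.

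**What to change.** - Add I25.2 to the myocardial infarction row and I25.5 to the heart failure row. The propensity score and the test-negative models then use the corrected flags as well.
- State which rows define each restricted analysis. For the section 4.8.1 restriction, include I42 in the heart-disease flag.
- For the restricted analyses, use the longest hospital-register look-back available to the study. If it stays at 10 years, describe these patients in sections 4.8.1 and 4.9 as having no hospital code for the condition within 10 years, in place of any history.

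The cost is a few codes, a wording change and a slightly smaller restricted subgroup. The protocol does not say how far back the study's hospital data reach, so the effort of a longer look-back cannot be judged from it; the wording change is available in any case.
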